8.4. Exploratory Analysis

DCR based on RECIST v1.1 will be correlated with DCR based on Immune-related Response Criteria (irRECIST) and summarized by descriptive statistics and comparative KM analysis.

PD-L1 and other biomarker expression in patients' tumors will be correlated with DCR and summarized by descriptive statistics.

DCR will be correlated with presence of PTEN mutation in patient's archived tumor and summarized by descriptive statistics.

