2.2.3. Exploratory Endpoints

- Correlation between DCR based on Immune-related Response Criteria (irRECIST) with that based on RECIST v1.1.
- Correlation between DCR with PD-L1 and other biomarker expression in patients' tumors.
- Correlation between DCR and PTEN mutation in patient's archived tumor

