5.2.4. Response Assessment

Tumor response will be assessed by CT or MRI scan of the chest, abdomen, and pelvis (CAP); image preparation and evaluation will follow the specifications provided in the RECIST version 1.1. Immune RECIST (irRECIST) will also be obtained. The same modality (CT or MRI) must be used at screening and throughout the study.

CT/MRI scans to be performed at the following frequency:

- ≤2 weeks prior to C1D1 (screening)
- followed by every 6 weeks for the first year; then every 12 weeks until disease progression or unacceptable toxicity. End of Treatment Visit CT/MRI should be performed only for those patients that discontinue treatment for a reason other than disease progression.

An unscheduled scan for suspected disease progression may be performed at any time. However, adherence to the planned imaging schedule is critical regardless of dose delays or unscheduled or missed assessments. Determination of disease progression for clinical management of patients on study will be assessed at the local site. If an initial observation

of objective response (CR or PR) is made, a confirmation scan should be done at 6 weeks after initial observation.

Conditions for Continuation of Treatment in the Presence of Increased Tumor Size by CT scan or MRI Indicating Progressive Disease by RECIST v1.1:

Treatment may be continued if:

1. There are no signs or symptoms indicating unequivocal progression.
2. There is no worsening of ECOG score attributable to progressive disease.
3. There is no tumor growth at critical sites that is life-threatening.
4. Patient signs an informed consent that he/she is aware of alternative therapies but wishes to defer these therapies.
5. There is clinical benefit, as determined by investigator

Table 3. Analyte Listing

Chemistry	Hematology	Coagulation	Urinalysis	Other Labs
Sodium	WBC	PT	Specific gravity	Pregnancy test
Potassium	RBC	PTT	pH	
Bicarbonate	Hemoglobin	INR	Blood	TSH, T3, T4
Chloride	Hematocrit		Protein	HIV
Total protein	MCV		Glucose	HBV sAg
Albumin	MCH		Ketones	HBV cAb
Calcium	MCHC		Microscopic	HCV Ab
Magnesium	RDW			Total Cholesterol
Phosphorus	Platelets			HDL
Glucose	Differential:			LDL
BUN	-Neutrophils			Triglyceride
Creatinine	-Lymphocytes			PD-1\PD-L1
Total bilirubin	-Monocytes			
Alkaline phosphatase	-Eosinophils			
AST (SGOT)	-Basophils			
ALT (SGPT)				
Amylase				
Lipase				

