8.3. Efficacy Analysis

The Efficacy Analysis Dataset includes all enrolled patients with measurable tumor per RECIST v1.1 at baseline who receive at least two doses of ABI-009 and had a follow-up CT scan/MRI.

The disease control rate (DCR; CR+PR+SD), objective response rate (ORR; CR + PR), progression free survival (PFS), recurrence-free survival (RFS) will be assessed by an local radiologic assessment using Response Evaluation Criteria in Solid Tumors (RECIST) v1.1.

The focus of the study is to estimate the DCR in patients treated with ABI-009 and nivolumab. Patients who progress before receiving ABI-009 will be replaced, and will not be included in the statistical analysis. The number and percentage of patients achieving disease control (CR, PR or SD) will be summarized.

Analysis of other efficacy endpoints, PFS at 4 months, RFS at 4 months, median PFS, median RFS and median OS will be assessed for all subtypes together, and separately in the five sarcoma subtypes with metastatic disease and locally advanced disease. Patients may be stratified further as locally advanced or metastatic. Patients in the locally advanced tumor subgroup may be clinically indicated to receive surgery if there is sufficient tumor shrinkage, which could introduce a bias in the assessment of the PFS at 4 months, median PFS, and OS. Recurrence-free survival (RFS) defined as progression free survival + absence of disease progression or recurrence after surgical resection has been added to the secondary endpoints to obviate this bias.

PFS, RFS and OS will be summarized using Kaplan-Meier (KM) analysis. The number of patients in each category is expected to be small; therefore, PFS at 4 months, RFS at 4 months, median PFS, and median OS for these patients will be summarized by descriptive statistics.

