8.8. Planned Methods of Analysis

8.8.1. General Considerations

A clinical study report will be generated for the primary analysis. The study report will be updated once the last data point is collected from the last patient that is required for primary, secondary, and/or exploratory analysis, as pre-specified in the protocol.

The analyses of all study objectives will be descriptive and hypothesis generating in nature.

Continuous variables will be summarized by the non-missing sample size (n), mean, standard deviation, first and third quartiles, minimum and maximum. Categorical variables will be summarized by the n and percent in each category.

Point estimates for efficacy endpoint incidences will be accompanied by a 2-sided 95% exact binomial CI (69).

Time to event endpoints will be summarized descriptively using the KM method (70). KM quartiles (when estimable) along with the 95% 2-sided CIs (71), the number of patients censored and the number of events will be provided. Kaplan Meier estimates will also be presented graphically.

No adjustments for multiplicity are planned for the analysis of the efficacy endpoints.

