8.8.2. General Considerations

The secondary efficacy endpoint, DCR, will be determined by a local radiologic assessment.

The primary analysis will evaluate the DCR in patients treated with ABI-009 and nivolumab by providing the number and proportion of patients achieving disease control along with an exact binomial 95% CI for the proportion.

DCR is defined as the proportion of patients who achieve a confirmed CR, PR or SD per RECIST v1.1. If an initial observation of objective response (CR or PR) is made, a confirmation scan should be done at 6 weeks after initial observation.

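### Section 8.4 lists a comparative Kaplan-Meier analysis for disease control by RECIST v1.1 against irRECIST, but disease control has no event time and the question is paired agreement

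*Combined protocol and SAP*

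**What the plan says.** The first exploratory endpoint in Section 2.2.3 is the "Correlation between DCR based on Immune-related Response Criteria (irRECIST) with that based on RECIST v1.1". Section 8.4 gives its analysis: the two DCRs are to be correlated and "summarized by descriptive statistics and comparative KM analysis". The Exploratory Analysis paragraph of the synopsis describes the same comparison with descriptive statistics alone.

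Four other places bear on it:

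- Section 8.8.2: "DCR is defined as the proportion of patients who achieve a confirmed CR, PR or SD per RECIST v1.1".
- Section 8.8.1, for proportions: "Point estimates for efficacy endpoint incidences will be accompanied by a 2-sided 95% exact binomial CI". For event times: "Time to event endpoints will be summarized descriptively using the KM method".
- Section 8.3: "PFS, RFS and OS will be summarized using Kaplan-Meier (KM) analysis". DCR is not on that list.
- Section 5.2.4, after tumor assessment by RECIST v1.1 is described: "Immune RECIST (irRECIST) will also be obtained". Both classifications therefore come from the same patients.

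No cross-tabulation or agreement measure is named for this endpoint. No time variable, event or censoring rule is given for the KM comparison.

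**The concern.** Kaplan-Meier needs a time origin, an event time and a censoring rule for each patient. Disease control is a yes/no classification and supplies none of these. A programmer working from Section 8.4 would have to drop the phrase or choose a time-to-event variable that the section does not name.

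The endpoint is also a question about pairs. Each patient is classified under both criteria, and a correlation between the two concerns how the classifications line up within patients. Two separate curves, like two separate percentages, do not carry that information.

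What is at stake is whether the first exploratory endpoint is reported in a form that answers it. The comparison has some practical interest here because Sections 2.3 and 5.2.4 allow treatment to continue, under conditions, after RECIST v1.1 progression.

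**Working it through.** The plan gives no sample size, power or agreement figure for this comparison, so there is nothing to reproduce. The check sets the sections side by side and then uses assumed data to show what a paired table would give.

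**Step 1. Variable against method.** Section 8.8.2 makes DCR a proportion. Section 8.8.1 gives proportions an exact binomial interval and gives KM to event times. Section 8.3 assigns KM to PFS, RFS and OS. Section 8.4 is out of line with all three, and with the synopsis.

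**Step 2. Separate summaries do not fix agreement.** Assume n = 40, with disease control in 24 patients by RECIST v1.1 (60%) and 28 by irRECIST (70%). Both tables below have exactly those totals.

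| Both | irRECIST only | RECIST only | Neither | Agreement |
|---|---|---|---|---|
| 24 | 4 | 0 | 12 | (24 + 12)/40 = 90% |
| 20 | 8 | 4 | 8 | (20 + 8)/40 = 70% |

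The totals would determine agreement only if every disagreement ran in one direction, which the plan does not state.

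**Step 3. What the paired table reports.** Assume about 60% controlled by both criteria, b patients controlled by irRECIST only and none by RECIST only. The sizes 28, 40 and 50 are the upper end of the Phase 2 range and the two ends of the total enrolment range; the plan does not say how many patients enter this comparison. Intervals are Clopper-Pearson. Kappa = (po − pe)/(1 − pe), where po is observed agreement and pe is chance agreement.

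| n | b | Agreement (95% CI) | Kappa |
|---|---|---|---|
| 28 | 2 | 26/28 = 92.9% (76.5 to 99.1) | 0.85 |
| 28 | 6 | 22/28 = 78.6% (59.0 to 91.7) | 0.50 |
| 40 | 4 | 36/40 = 90.0% (76.3 to 97.2) | 0.78 |
| 50 | 2 | 48/50 = 96.0% (86.3 to 99.5) | 0.92 |
| 50 | 6 | 44/50 = 88.0% (75.7 to 95.5) | 0.74 |

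For the n = 40 row, po = 0.90 and pe = 0.70 × 0.60 + 0.30 × 0.40 = 0.54, so kappa = 0.36/0.46 = 0.78.

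The exact McNemar p-value with all b disagreements in one direction is 2 × 0.5^b: 0.50, 0.125 and 0.031 for b = 2, 4 and 6, whatever n is. A formal test would thus add little unless disagreements were fairly numerous.

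**Step 4. Pairing, if a difference were ever estimated or tested.** In the n = 40 row the DCR difference is 4/40 = 10 points. Treating the two DCRs as independent gives SE = √(0.70 × 0.30/40 + 0.60 × 0.40/40) = 10.6 points. The paired SE is √(4 − 4²/40)/40 = 4.7 points, so the unpaired interval would be about 2.2 times as wide.

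The same caution applies to curves. An ordinary log-rank test at nominal 5% was simulated on two sets of times from the same patients with no true difference (2,000 runs per setting, uncensored exponential times, correlation on a latent normal scale). Rejection rates for n = 28 and n = 50 were 7.1% and 5.0% at correlation 0, 1.3% and 1.1% at 0.5, and at most 0.05% at 0.8 and 0.95. These results apply only to a formal comparison, which the plan does not specify.

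**The case against.** The strongest reply is that this is one loose phrase in an exploratory section. Much of that stands.

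- A reader might infer that the endpoint has no usable method. The documents do not support that. Section 8.4 also plans a correlation and descriptive statistics, and Section 8.8.1 summarizes categorical variables by count and percent. A cross-tabulation fits within those words, although none is named. Only the KM part fails.
- A reader might infer that the reported error bars will be wrong or too wide. No test, hazard ratio or interval for a difference is planned, and Sections 8.6 and 8.8.1 call all analyses descriptive. Comparative may mean no more than two curves on one page, and each curve's own confidence interval remains valid when the same patients supply both. The figures in Step 4 are therefore conditional.
- A reader might say that only discordant patients carry information. That holds for a McNemar test. Percent agreement and kappa use the concordant patients too.
- A reader might take pseudo-progression as the stated question. The plan asks only for correlation between the criteria.
- KM curves of PFS or RFS by criterion may have been intended. Section 2.2.2 and the synopsis efficacy paragraph assess both under RECIST v1.1 and irRECIST. This reading is plausible, but Section 8.4 names DCR, Section 8.3 names RECIST v1.1 only, and Section 8.8.3 gives no irRECIST event or censoring rule. Section 5.2.4 and the Table 2 imaging footnote schedule scans until progression, so follow-up beyond RECIST v1.1 progression may depend on whether treatment continues. Such curves would need those rules written down.

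**Conclusion.** The point holds in a limited form. The comparative KM analysis in Section 8.4 cannot be carried out on DCR as Section 8.8.2 defines it. It conflicts with the plan's own allocation of methods in Sections 8.3 and 8.8.1 and with the synopsis. Nor would separate curves show patient-level agreement between criteria applied to the same patients.

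Severity is low. The analysis is exploratory and descriptive, and neither the MTD nor the main DCR estimate depends on it. The conclusion rests on the text alone. The agreement, kappa and standard error figures rest on assumed tables, because the plan gives no expected number of disagreements.

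**What to change.** 1. Delete the comparative KM analysis from the DCR sentence in Section 8.4.
2. In its place specify a paired cross-tabulation of RECIST v1.1 by irRECIST, with percent agreement and its exact 95% CI. Kappa, or an exact paired interval for the DCR difference, is optional.
3. Use the same wording in the synopsis and Section 8.4.
4. If KM curves of PFS or RFS by each criterion are wanted, list them as a separate item with the irRECIST event and censoring rules, including how follow-up after RECIST v1.1 progression is handled. Show them descriptively. Any formal comparison of the two curves must allow for pairing.

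For items 1 to 3 the cost is wording only: the plan already has both classifications obtained, so no new data are needed. Item 4 also needs the event and censoring rules to be written.

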8.5. Covariates and Subgroups

Up to 20 clinical indications will be studied, including Ewing's sarcoma, PEComa, epithelioid sarcoma, desmoid tumor, chordoma, non-small cell lung cancer, small cell lung cancer, urothelial carcinoma, melanoma, renal cell carcinoma, squamous cell carcinoma of head and neck, hepatocellular carcinoma, classical Hodgkin's lymphoma, MSI-H/dMMR metastatic colorectal cancer, and tumors with genetic mutations sensitive to mTOR inhibitors, as well as those with metastatic disease and those with locally advanced disease for which surgery is not an option. The subgroups of patients will be assessed together and as subgroups for the efficacy endpoints.

In addition, the following covariates may be used to examine efficacy and/or safety in subgroup or covariate analyses, if sufficient number of patients are enrolled in the subgroups:

- Gender (male and female)
- Age at enrollment (<65 vs ≥65 and <75 vs ≥75 years)
- ECOG Performance Status at baseline (0 vs 1)

- Time from initial diagnosis to enrollment

8.6. Sample Size Considerations

The analyses of all study objectives is descriptive and hypothesis generating in nature. The sample size will not be enough to make any statistical conclusions about efficacy or safety, but will be useful for planning future Phase 2 clinical trials.

8.7. Primary Analysis

The objective of the primary analysis is to address all study objectives and it will be conducted when all patients have had the opportunity to be treated for at least 6 months. All primary, secondary, and exploratory efficacy and safety analyses will be conducted at the time of the primary analysis.

8.8. Planned Methods of Analysis

8.8.1. General Considerations

A clinical study report will be generated for the primary analysis. The study report will be updated once the last data point is collected from the last patient that is required for primary, secondary, and/or exploratory analysis, as pre-specified in the protocol.

The analyses of all study objectives will be descriptive and hypothesis generating in nature.

Continuous variables will be summarized by the non-missing sample size (n), mean, standard deviation, first and third quartiles, minimum and maximum. Categorical variables will be summarized by the n and percent in each category.

Point estimates for efficacy endpoint incidences will be accompanied by a 2-sided 95% exact binomial CI (69).

Time to event endpoints will be summarized descriptively using the KM method (70). KM quartiles (when estimable) along with the 95% 2-sided CIs (71), the number of patients censored and the number of events will be provided. Kaplan Meier estimates will also be presented graphically.

No adjustments for multiplicity are planned for the analysis of the efficacy endpoints.

8.8.2. General Considerations

The secondary efficacy endpoint, DCR, will be determined by a local radiologic assessment.

The primary analysis will evaluate the DCR in patients treated with ABI-009 and nivolumab by providing the number and proportion of patients achieving disease control along with an exact binomial 95% CI for the proportion.

DCR is defined as the proportion of patients who achieve a confirmed CR, PR or SD per RECIST v1.1. If an initial observation of objective response (CR or PR) is made, a confirmation scan should be done at 6 weeks after initial observation.

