Follow-up period is the on-study time period after the EOT Visit. All patients that discontinue study drug and have not withdrawn full consent to participate in the study will continue in the follow-up phase for survival and initiation anticancer therapy. Follow up will continue approximately every 12 weeks (+/- 3 weeks), until death, withdrawal of consent, or the study closes, whichever is the earliest. This evaluation may be made by record review and/or telephone contact.

Study Treatment

Patients will receive nivolumab 3 mg/kg as IV infusion over 30 min every 3 weeks (Day 1 of every 21-day cycle), followed by escalating doses of ABI-009 30, 45, 75 mg/m² for 2 of every 3 weeks by IV infusion over 30 minutes. ABI-009 dosing will start after 2nd nivolumab dose and to be administered on Day 8 and Day 15 of every cycle beginning in Cycle 2. Patients will continue therapy until unequivocal clinical disease progression, unacceptable toxicity, or until in the opinion of the investigator the patient is no longer benefiting from therapy, or at the patient's discretion.

Overview of Key Safety Assessments

Safety and tolerability will be monitored through continuous reporting of treatment-emergent and treatment-related adverse events (AEs), AEs of special interest, laboratory abnormalities, and incidence of patients experiencing dose modifications, dose delay/dose not given, dose interruptions, and/or premature discontinuation of IP due to an AE. All AEs will be recorded by the investigator from the time the patient signs informed consent until 28 days after the last dose of IP. Adverse events will be graded by National Cancer Institute (NCI) Common Terminology Criteria for Adverse Events (CTCAE) v4.03.

Physical examination, vital signs, laboratory assessments (e.g., serum chemistry, hematology), and ECOG performance status will be monitored. All SAEs (regardless of relationship to IP) will be followed until resolution. Local laboratory analysis will be performed as per study schedule.

The MTD for ABI-009 will be determined, and will be used in the Phase 2 part of the study.

Overview of Key Efficacy Assessments

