Patients will be evaluated for disease control rate [complete response (CR), partial response (PR), and stable disease (SD)], or progressive disease (PD) by CT imaging. Contrast enhanced MRI can also be used, as long as the same modality is used throughout the study. Baseline scan results can be accepted from outside institutions, but must be done within 4 weeks of starting therapy and must include (as clinically indicated), chest abdominal, and pelvic CT or MRI. The first response assessment by CT or MRI scans documenting target lesions will be done 6 weeks after first treatment and should be repeated every 6 weeks for the first year, then every 12 weeks thereafter until the end of treatment. If an initial observation of objective response (CR or PR) is made, a confirmation scan should be done at 6 weeks after initial observation. Scans should continue on schedule regardless of delays in ABI-009 dosing.

The efficacy endpoints, DCR (CR, PR and SD), OR (CR + PR), PFS, and RFS will be determined by a local radiologic assessment using RECIST v1.1. After end of treatment, patients will be followed for survival every 12 weeks (+/- 3 weeks), or more frequently as needed, until death, withdrawal of consent, or the study closes, whichever is the earliest.

Statistical Considerations

Safety Analyses:

Demographic and baseline information (e.g., extent of prior therapy) on study patients will be tabulated. The number of patients studied for the Phase 1 (dose escalation) part of study could range from 12 to 18 evaluable patients, and 22-28 evaluable patients for the Phase 2 (dose expansion) part of the study.

For the Phase 1 part of the study, the following information will be reported for all adverse events observed in the study: dose level, type (organ affected or laboratory determination, such as absolute neutrophil count), severity (by NCI Common Terminology Criteria for Adverse Events (CTCAE) Version 4.03 and most extreme abnormal values for laboratory determinations) and relatedness to study treatment. For each dose the number and percentage of patients experiencing any grade 3, 4, or 5 adverse event will be reported, as well as the number and percentage of patients who experienced selected specific types of adverse events. In addition, the DLTs will be summarized by dose level and the MTD will be determined.

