A large randomized placebo-controlled phase III trial evaluated the mTOR inhibitor ridaforolimus to assess maintenance of disease control in advanced sarcomas after benefit from prior chemotherapy (16). Patients with metastatic soft tissue or bone sarcomas who achieved objective response or stable disease with prior chemotherapy were randomly assigned to receive ridaforolimus 40 mg or placebo once per day for 5 days every week. Primary end point was progression-free survival (PFS); secondary end points included overall survival (OS), best target lesion response, safety, and tolerability. A total of 711 patients were enrolled, and 702 received blinded study drug. Ridaforolimus treatment led to a modest, although significant, improvement in PFS per independent review compared with placebo (hazard ratio [HR], 0.72; 95% CI, 0.61 to 0.85; $P < .001$; median PFS, 17.7 v 14.6 weeks). Ridaforolimus induced a mean 1.3% decrease in target lesion size versus a 10.3% increase with placebo ($P < .001$). Median OS with ridaforolimus was 90.6 weeks versus 85.3 weeks with placebo (HR, 0.93; 95% CI, 0.78 to 1.12; $P = .46$). Adverse events (AEs) more common with ridaforolimus included stomatitis, infections, fatigue, thrombocytopenia, noninfectious pneumonitis, hyperglycemia, and rash. Grade 3 AEs were more common with ridaforolimus than placebo (64.1% v 25.6%). Conclusion: Ridaforolimus delayed tumor progression to a small statistically significant degree in patients with metastatic sarcoma who experienced benefit with prior chemotherapy. Toxicities were observed with ridaforolimus, as expected with mTOR inhibition. These data provide a foundation on which to further improve control of sarcomas.

Other mTOR inhibitors, including sirolimus and everolimus, have been tested or are being tested in clinical trials for advanced soft tissue sarcoma. For example, sirolimus, is currently approved for immunosuppression following organ transplantation. However, there is increasing interest in its role as a neoplastic agent. In a report of four cases of progressive metastatic sarcoma in patients who have progressed after 2–6 lines of chemotherapy, treatment with sirolimus resulted in minor radiographic improvement in three cases (17). Myxoid chondrosarcoma has also been reported to respond well to sirolimus in combination with cyclophosphamide (18).

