follow-up CT scans or MRIs were performed after every 2 cycles of the sequential chemo-/immuno-therapy. Tumor responses were assessed by RECIST v1.1 and immune-related response criteria (irRC). Histologic subtypes include malignant fibrous histiocytoma / undifferentiated pleomorphic sarcoma (n = 6), leiomyosarcoma (n = 3), synovial sarcoma (n = 2), myxoid liposarcoma (n = 2) and chondrosarcoma (n = 1). All patients had metastatic disease and a median of 4 lines of prior chemotherapy. Safety analysis: Grade 3 treatment emergent adverse events include anemia (n=1), fatigue (n = 1), decreased platelet count (n=1), and increased creatine kinase (n=1). These AEs have been reported with trabectedin use. No immune-related adverse event has been observed so far. Efficacy analysis: Thirteen patients received 2 cycles of sequential chemo-/immuno-therapy, had follow-up CT scan or MRI, and were evaluated for objective response (OR), best overall response rate, (BORR), disease control rate (DCR), progression-free survival (PFS) and overall survival (OS). There were 2 partial responses (PR), with one biopsied nodule showing >90% liquefaction necrosis, 8 stable disease (SD) and 3 progressive disease (PD), with best overall response rate (BORR) of 15.3%, DCR of 76.9%, median PFS of >8 weeks (range: 8-21 weeks), and median OS of >8 weeks (12.3->21 weeks). To our knowledge, this study is the first to explore sequentially administered chemo-/immuno-therapy in patients with advanced STS. The initial data suggest that paired administration of trabectedin and nivolumab is safe. We continue to evaluate for safety as well as synergistic activity based on their mechanisms of action on the tumor-immune microenvironment (27).

1.1.4 Strategies to improve the efficacy of immune checkpoint inhibitors in other clinical indications.

Recently, several studies focused in modifying the tumor-immune microenvironment (TME) with small molecules that increase the number of activated T cells exerting tumoricidal activity and/or suppressing growth promoting macrophages in the TME. These drugs include microbiota modifiers, drugs targeting co-inhibitory receptors, anti-angiogenic therapeutics, small molecules, and oncolytic viruses.

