6. DESCRIPTION OF STUDY TREATMENTS (ABI-009/NIVO)

6.1. ABI-009/Nivolumab Dosage, Administration, and Schedule

For the Phase 1 part of study, patients will receive nivolumab 3 mg/kg as IV infusion over 60 min every 3 weeks, followed by escalating doses of ABI-009 56, 75, 100 mg/m² for 2 of every 3 weeks by IV infusion over 30 minutes. ABI-009 will start on Day 8 of Cycle 2. If DLT develops in more than 1 patient at Dose 56 mg/m², the dose will be de-escalated to 45 mg/m² and to 30 mg/m² if DLT develops at 45 mg/m². Patients will continue therapy until unequivocal clinical disease progression, unacceptable toxicity, or until in the opinion of the investigator the patient is no longer benefiting from therapy, or at the patient's discretion.

For the Phase 2 part of study, patients will receive nivolumab 3 mg/kg as IV infusion over 30 min every 3 weeks, followed by ABI-009 at the MTD dose for 2 of every 3 weeks by IV infusion over 30 minutes. ABI-009 will start on Day 8 of Cycle 2. Patients will continue therapy until unequivocal clinical disease progression, unacceptable toxicity, or until in the opinion of the investigator the patient is no longer benefiting from therapy, or at the patient's discretion.

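### DCR has no minimum duration for stable disease and no rule for confirming it, so a single SD at week 6, 14 days after the first ABI-009 dose, can count as disease control

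*Combined protocol and SAP*

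**What the plan says.** **Definition.** Section 8.8.2 (the second of the two subsections titled General Considerations): "DCR is defined as the proportion of patients who achieve a confirmed CR, PR or SD per RECIST v1.1". The next sentence there is the only confirmation rule: "If an initial observation of objective response (CR or PR) is made, a confirmation scan should be done at 6 weeks after initial observation". Table 2 (footnote l), Section 5.2.4 and the synopsis repeat that rule, again only for CR or PR. Section 8.3 and the synopsis (Efficacy Analyses) define DCR as CR+PR+SD without the word confirmed. No section gives a minimum duration for SD.

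**Timing.** Nivolumab is given "every 3 weeks (Day 1 of every 21-day cycle"). Section 6.1: "ABI-009 will start on Day 8 of Cycle 2". The synopsis: "The first response assessment by CT or MRI scans documenting target lesions will be done 6 weeks after first treatment". Table 2 counts the scans from Cycle 1 Day 1, every 6 weeks in the first year.

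**Role of DCR.** MTD is the primary endpoint and DCR is secondary. Section 8.3 nevertheless makes estimating DCR the study's focus, and Section 8.8.2 puts DCR in the primary analysis. All three exploratory endpoints in Section 2.2.3 (irRECIST, PD-L1 and other biomarkers, PTEN) are correlations with DCR.

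**Who is counted.** Under Section 8.3, patients who progress before ABI-009 are replaced and left out. The efficacy set needs at least two ABI-009 doses and a follow-up scan.

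**The concern.** Two analysts with the same scans could report different DCRs. One would count a single SD at week 6. The other would read confirmed as covering SD and ask for a second scan. The text does not settle which is right.

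Under the first reading, the endpoint rewards a tumour for not growing past the progression threshold in six weeks, the first four of them before any ABI-009. Eligibility (Section 3.2) does not require documented progression at entry. An SD at that scan would therefore mostly reflect how fast the tumour was already growing, plus nivolumab alone. The DCR itself and every DCR-based biomarker correlation would carry that weakness. Section 8.6 says the results are meant to help plan later Phase 2 trials, so the figure will be used.

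**Working it through.** The plan states no expected DCR, null rate or DCR-based sample size, so there is no planned figure to reproduce.

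**1. Days from Cycle 1 Day 1 (day 1)**
- Cycle 2 Day 1 = 1 + 21 = day 22.
- First ABI-009 dose, Cycle 2 Day 8 = 22 + 7 = day 29. Second dose, Cycle 2 Day 15 = day 36.
- Week-6 scan = 1 + 42 = day 43. Gap from first ABI-009 dose = 43 − 29 = 14 days; from second dose, 7 days.
- With the Table 2 windows (visits ±2 days, scans ±3 days), the first gap runs from 40 − 31 = 9 to 46 − 27 = 19 days.
- Share of the interval before ABI-009 = 28/42 = two thirds.
- Week-12 scan = 1 + 84 = day 85, which is 85 − 29 = 56 days (8 weeks) after the first ABI-009 dose.

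**2. Illustration from the placebo arm in Section 1.1.1** ("median PFS, 17.7 v 14.6 weeks", ridaforolimus v placebo). Assuming exponential PFS, S(t) = 0.5^(t/median):

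| Source | Median (weeks) | S(6) | S(12) | S(24) |
|---|---|---|---|---|
| Phase III, placebo | 14.6 | 75.2% | 56.6% | 32.0% |
| Phase III, ridaforolimus | 17.7 | 79.1% | 62.5% | 39.1% |
| Phase II, ridaforolimus | 15.3 | 76.2% | 58.1% | 33.7% |

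On the placebo median, the two readings of DCR differ by 75.2 − 56.6 = 18.6 points. In 28 patients that is about 21 against 16 successes (28 × 0.752 = 21.1; 28 × 0.566 = 15.8).

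**3. How far the week-6 figure moves**
- Weibull PFS with the same 14.6-week median, S(6) = 0.5^((6/14.6)^k): k = 0.7 gives 69%, k = 2 gives 89%.
- Pembrolizumab alone (Section 1.1.2), S(6) = √S(12) if exponential. Soft tissue sarcoma: 12-week PFS 55% gives 74% (from the quoted 95% limits, 65% to 84%). Bone sarcoma: 28% gives 53% (37% to 64%).
- The point values therefore span roughly 50% to 90%.

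**4. Leaving out early progressors.** If every progression before ABI-009 were detected and removed, the placebo-median value at week 6 would be S(6)/S(4) = 0.5^(2/14.6) = 91%. Removing progressions up to the second dose at week 5 gives S(6)/S(5) = 95%. No scan is scheduled before week 6, so detection would be incomplete and the value would lie between 75% and these figures.

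**5. Precision.** Exact 95% intervals: 21/28 = 75% (55% to 89%); 16/28 = 57% (37% to 76%).

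**The case against.** **Confirmed may cover SD.** The wording in Section 8.8.2 can be read that way, Section 1.2.4 uses confirmed SD for the earlier ABI-009 study, and scans recur every 6 weeks, so a second scan is already available. This stands to the extent that a single-scan rule is not settled by the text. It does not supply a rule, and Section 8.3 and the synopsis drop the word.

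**A reader might infer that a DCR near 75% is to be expected from natural course alone.** The documents do not support that. The placebo arm was selected: "Patients with metastatic soft tissue or bone sarcomas who achieved objective response or stable disease with prior chemotherapy were randomly assigned". This trial covers up to 20 indications (Section 8.5), and for most of them the documents give no untreated figure. The bone sarcoma figure implies about 53%, even on a PD-1 inhibitor. Nor do the documents give growth rates for desmoid tumor or chordoma that would support a figure for those types.

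**A reader might also take the site's earlier result ("DCR of 76.9%, median PFS of >8 weeks") as bearing this out.** It does not. It is 10/13 (exact 95% interval 46% to 95%), with trabectedin as partner. Scans followed every two cycles of 3 to 4 weeks after a 3-week lead-in, so the first came about 3 + 6 = 9 to 3 + 8 = 11 weeks after first dose.

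**Other endpoints help.** ORR and PFS rates at 3, 6, 9 and 12 months are planned, and the 3-month rate sits close to week 12. This is a fair point and lowers the stakes, but it does not define DCR or repair the correlations built on it.

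**A later cutoff does not prove benefit.** Modelled placebo and ridaforolimus differ by 79.1 − 75.2 = 3.9 points at week 6 and only 62.5 − 56.6 = 5.9 at week 12. This stands. The gain is a defined endpoint with longer exposure to the combination, not attribution.

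**Conclusion.** The point holds as a defect of definition and timing. SD has no minimum duration, its confirmation has no operation behind it, and under the plain CR+PR+SD reading one SD read 14 days after the first ABI-009 dose counts as disease control. The choice of reading could move the reported DCR by about 19 points. That size rests on exponential PFS and on a placebo arm that does not represent this trial's population, so it is an illustration and not a forecast.

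A stronger conclusion, that DCR is useless or that the trial cannot describe disease control at all, goes too far. The analyses are declared descriptive, no DCR threshold triggers a decision, MTD is the primary endpoint, and PFS rates to 12 months will be reported. The matter should be fixed because Section 8.3 gives DCR a central place, but it does not undermine the trial's primary objective.

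**What to change.** In Section 8.8.2, Section 8.3 and the synopsis:

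- Define DCR as confirmed CR or PR, or SD maintained at the scheduled week-12 scan, meaning two consecutive non-PD scans, the second about 8 weeks after the first ABI-009 dose.
- State that PD at week 6 or week 12 without a confirmed response is not disease control.
- State how patients are classified if they are resected before week 12 (surgery is possible after three cycles, 3 × 3 = 9 weeks) or have no evaluable week-12 scan.
- Apply the same timing rule to DCR by irRECIST, so that the planned comparison with RECIST v1.1 is like for like.
- Label any week-6 figure as best overall response.

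The week-12 point is chosen because it is the next scheduled scan, so no visit or scan is added. The cost is an edit to the text and a lower headline DCR. The rule does not remove the effect of leaving out patients who progress before ABI-009: on the placebo median, S(12)/S(4) = 0.5^(8/14.6) = 68%, against 57% without that exclusion. The report should state this next to the DCR.
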